 - Gestational diabetes, well-controlled on medications (with or without diet or exercise): i.e. when normoglycemia is maintained (fasting or preprandial blood glucose values <95 mg/dL [5.3 mmol/L], and/or postprandial blood glucose concentration <140 mg/dL [7.8 mmol/L] at 1 hour and/or postprandial blood glucose concentration: <120 mg/dL [6.7 mmol/L] at 2 hours).
 - Gestational hypertension, well-controlled on diet or medications below 160/110 mmHg.
 - Pre-eclampsia without severe features (i.e. eclampsia, severe hypertension [$>160/110$ mmHg], organ dysfunction, unstable or complicated by Hemolysis, Elevated Liver enzymes, and Low Platelets [HELLP] syndrome).
 - Fetal Growth Restriction in singleton pregnancies, with normal umbilical artery (UA) Doppler and estimated fetal weight 3 to 10th percentile for gestational age.
 - History of threatened preterm labor in the current pregnancy, with no cervical dilation greater than 2 cm or effacement exceeding 50%, and/or no progressive change in cervical dilation or effacement detected by serial examinations, when maternal participant is asymptomatic (i.e. no vaginal bleeding or uterine contractions or amniotic fluid loss).
 - Uncomplicated twin gestation.
- Pregnant females at 24^{0/7} to 36^{0/7} weeks of gestation at the time of study intervention administration (Day 1), as established by:
 - Last menstrual period (LMP) date corroborated by first or second trimester ultrasound examination (U/S) (i.e. at or before 28 weeks of gestation).
 - first or second trimester U/S only, if LMP is unknown/uncertain.
 - Certain LMP, corroborated by an U/S performed after 28 weeks of gestation is also acceptable.

Notes: If pregnancy resulted from assisted reproductive technologies, LMP date may be replaced by intrauterine insemination (IUI) or embryo-transfer (ET) date. Refer to Section 10.8 for guidance on gestational age assessment.

The level of diagnostic certainty of the gestational age should be established by using the GAIA gestation age assessment tool (Section 10.8).

- Participants who are willing to provide cord blood.

- Willing to have their offspring followed-up after delivery for a period of 12 months.
- Participants who do not plan to give their offspring for adoption or place the child in care.

Note that women whose pregnancies resulted from assisted reproductive technologies may be enrolled if they meet all inclusion criteria and none of the exclusion criteria.

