5.2.1. Maternal participants

5.2.1.1. Medical conditions

- History of any reaction or hypersensitivity likely to be exacerbated by any component of the study intervention.
- Hypersensitivity to latex.
- Any pre-existing medical conditions or obstetric complications in the current pregnancy that, based on the investigator's clinical judgment, are poorly controlled and/or with clinical evidence of a non-reassuring fetal status and/or are likely to result in delivery within 7 days after study intervention administration and/or when the timing of planned delivery is within 7 days after study intervention administration and/or acute conditions requiring immediate medical attention for maternal stabilization and/or treatment.
- A multiple pregnancy with 3 or more fetuses.

- Complicated twin gestation (e.g twin to twin transfusion syndrome or fetal growth restriction).
- Placenta Accreta Spectrum, including placenta increta, percreta, and accreta.
- Fetal structural defects or genetic abnormalities that affect (or are likely to affect) fetal health or survival during the first year of life.
- Known or suspected impairment of the immune system or immunodeficiency syndrome other than HIV.
- Lymphoproliferative disorder or malignancy within 5 years before study dose administration (excluding effectively treated non-melanoma skin cancer).
- Any illness of the mother or conditions of the fetus that, in the investigator's judgment, may substantially interfere with the maternal participant's ability to comply with study procedures, or could increase the risks to the mother or the fetus, or could preclude the evaluation of the participant's data.
- Any other clinical condition that, in the opinion of the investigator, might pose additional risk to the participant due to participation in the study, as determined by medical history, physical examination or laboratory screening tests.
- Women with any diagnosis, condition, treatment, or other factor that, in the opinion of the investigator, has the potential to affect or confound assessments of immunogenicity or safety
- Any conditions which, in the investigator's opinion, would increase the risks of study participation to the unborn infant.

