3. ANALYSIS SETS

3.1. Definition

Table 3 Maternal Participants

Analysis Set	Definition / Criteria	Analyses Evaluated
Enrolled	All maternal participants who completed the informed consent process and signed the informed consent form and were determined as eligible for study participation.	Study Population
Exposed	All maternal participants who received 1 dose of a study intervention. The allocation in a group is done in function of the administered intervention.	Safety
Full Analysis Immunogenicity	All maternal participants in the Exposed set who have at least one post-dosing immunogenicity data. It will be defined by timepoint, e.g. FAS at Day 31	Immunogenicity
Per-Protocol Immunogenicity	All maternal participants in the Full Analysis (Immunogenicity) minus participants with protocol deviations that lead to exclusion. The analysis will be done according to the study interventions that participants received. It will be defined by timepoint, e.g. PPS at Day 31.	Immunogenicity
Solicited Safety	All maternal participants in the Exposed set who have solicited safety data.	Safety

FAS = Full Analysis Set; PPS = Per Protocol Set

Table 4 Infant Participants

Analysis Set	Definition / Criteria	Analyses Evaluated
Exposed	Infants live-born to exposed maternal participants, whose parents/LARs completed the informed consent process and signed the informed consent form.	Safety
Full Analysis Immunogenicity	All infant participants in the Exposed set who have at least one post-delivery/birth immunogenicity data. The analysis will be done according to the study intervention that maternal participants received. It will be defined by timepoint, e.g. FAS at Day 31	Immunogenicity
Per-Protocol Immunogenicity	All infant participants in the Full Analysis (Immunogenicity) set minus those who (a) were born less than 4 weeks post-maternal participant dosing and/ or (b) have protocol deviations that lead to exclusion. It will be defined by timepoint, e.g. PPS at Day 31	Immunogenicity

FAS = Full Analysis Set; PPS = Per Protocol Set

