4.1.1. General Methodology

Participants who prematurely withdrew from study will not be replaced.

Unless otherwise specified, continuous data will be summarized using descriptive statistics: n, mean, standard deviation (SD), median, minimum and maximum. Categorical data will be summarized as the number and percentage of participants in each category.

95% confidence interval (CI) for proportion will be based on exact Clopper-Pearson confidence interval [[Clopper, 1934](#)].

95% CI for group difference in proportion will be based on Miettinen and Nurminen confidence interval [[Miettinen, 1985](#)].

95% CI for GMT(C) will be based on a back transformation of student confidence interval for the mean of log-transformation.

95% CI for GMT(C) ratio between groups will be based on a back transformation of confidence interval for the mean difference on log-transformation.

For a given participant and given immunogenicity measurement, missing or non-evaluable measurements will neither be imputed nor be replaced, and therefore will not be included in immunogenicity analysis.

For between group statistical modelling analysis, participants having a result at both the baseline and the considered timepoint will be included in the analysis.

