4.2.2. Immunogenicity

4.2.2.1. Analysis of immunogenicity planned in the protocol

The primary analysis for immunogenicity will be based on the PPS for analysis of immunogenicity.

	Primary Immunogenicity Endpoints	Statistical Analysis Methods
Maternal participants	
 • Humoral immune responses at pre-dosing (Day 1) and at delivery: 
 – RSVPreF3 IgG-specific antibody concentrations – Neutralizing antibody titers against RSV-A 	
For each assay, at each timepoint and by study group and age category (<18 years; ≥ 18 years; overall):
 
 • Antibody titers/concentrations will be displayed using reverse cumulative curves. • GMTs/ GMCs will be tabulated with 95% CI and represented graphically. • GMR of antibody titers/concentrations at delivery over pre-dosing will be tabulated with 95% CI. 
Between group evaluation in terms of RSVPreF3 IgG-specific antibody concentrations and neutralizing antibody titers against RSV-A will be performed at delivery using an ANCOVA model on the logarithm₁₀ transformation of the concentrations/titers, and including the pre-dosing logarithm₁₀ transformation of the concentrations/titers, the study intervention, gestational age at the time of study intervention administration (<28^{0/7}; ≥ 28^{0/7} weeks), and the interval between dosing and delivery as covariates if needed.

Cord blood/placental transfer	
Ratio between cord blood* and maternal RSVPreF3 IgG-specific antibody concentrations at delivery.
 
*or infant blood sample collected within 72 hours after birth (if no cord blood sample can be obtained).
	
 • Geometric mean of placental transfer ratio will be tabulated with 95% CI by study group. • Percentage of infants with placental transfer ratio ≥ 1 will be tabulated with exact 95 % CI by study group.

	Primary Immunogenicity Endpoints	Statistical Analysis Methods

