4.3.3. Sensitivity analyses

For primary and secondary immunogenicity endpoints, between study group comparisons will also be explored through statistical modelling. This analysis is exploratory.

For the analysis of maternal participants at each time point (Day 31, Delivery), the ANCOVA model will be explored and fitted via the proc GML procedure according to the following code:

```
PROC GLM data=adis_moth;
  BY atptn atpt;
  CLASS tr01aga gagevg1 agegr3;
  MODEL aval = base tr01aga gagevg1 agegr3 vacdel;
  LSMEANS tr01aga/pdiff cl alpha=0.05;
RUN;
```

where aval represents the log-transformed antibody value of the immunogenicity variable at a given post baseline timepoint, group indicates the study group, gagevg1 is the gestational age category at study intervention administration ($<28^{0/7}$, $\geq 28^{0/7}$ weeks), agegr3 is the age category at study intervention administration (<18 years and ≥ 18 years), vacdel is the interval between vaccination and delivery (days). The inclusion of age category at study intervention administration, interaction term between age category and gestational age category and interval between study intervention administration and delivery in the model depends on the availability of the variables (vacdel may not be available at Day 31 analysis) and the necessity, therefore, the above SAS code serves as a reference and may be adjusted according to the analysis needs. Other possible co-variables which could be included in the model, but not limited to, are pre-existing HIV infection status, CD4 count, COVID-related complications.

For the analysis of infants at each time point (cord blood at Delivery, Day 43 post-birth, Day 121 post-birth, and Day 181 post-birth), similar model will be explored:

```
PROC GLM data=adis;
  BY atptn atpt;
  CLASS tr01aga gagevg1 gagebg1 agegr3;
  MODEL aval = base tr01aga gagevg1 gagebg1 agegr3;
  LSMEANS tr01aga/pdiff cl alpha=0.05;
RUN;
```

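### Where both twins of a mother give a birth sample, the infant antibody and placental-transfer intervals ignore the pairing and are slightly too narrow

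*SAP*

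**What the plan says.** - **Eligibility.** Protocol 5.1.1 lists "Uncomplicated twin gestation" among the qualifying obstetric conditions for adults. Protocol 5.2.1.1 excludes "A multiple pregnancy with 3 or more fetuses" and complicated twins, so a mother contributes at most two infants.
- **Analysis sets.** SAP 3.1 defines the infant Exposed set as "Infants live-born to exposed maternal participants, whose parents/LARs completed the informed consent process and signed the informed consent form" and the infant Full Analysis Set as "All infant participants in the Exposed set who have at least one post-delivery/birth immunogenicity data". The Per-Protocol set removes births less than 4 weeks after dosing and protocol deviations. No elimination code in SAP Tables 6 and 8 removes a second twin.
- **Interval methods.** SAP 4.1.1: "95% CI for GMT(C) will be based on a back transformation of student confidence interval for the mean of log-transformation" and "95% confidence interval (CI) for proportion will be based on exact Clopper-Pearson confidence interval". It names no separate method for the geometric mean transfer ratio; I take the log-scale Student interval to apply.
- **Primary infant endpoints.** SAP 4.2.2.1 plans GMT/GMC at birth with 95% CI, the geometric mean transfer ratio with 95% CI, and: "Percentage of infants with placental transfer ratio ≥ 1 will be tabulated with exact 95 % CI by study group". It also lists an infant ANCOVA.
- **Model code.** SAP 4.3.3 fits infants with PROC GLM, "MODEL aval = base tr01aga gagevg1 gagebg1 agegr3". The baseline is the mother's pre-vaccination value. There is no mother identifier and no random or repeated term.
- **Multiples.** The one rule on multiples, in SAP 4.3.1.2.4, counts stillbirths, preterm births and spontaneous abortions per pregnancy. Nothing equivalent covers antibody data.

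**The concern.** Twins share the mother's allocation, dosing date, delivery and pre-dose antibody level. In the transfer ratio they also share the maternal denominator. Their results should be positively correlated, and an interval built on independent infants then credits a pair with more information than it holds. The endpoints concerned are primary. Because the trial tests no hypothesis, the estimates and their intervals are all it reports on these questions, so the stated precision should be right.

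**Working it through.** **1. The plan's own precision figure.** Protocol Table 21 and SAP Table 14 give log10 half-widths of 0.056 (SD 0.3) and 0.074 (SD 0.4) for the maternal RSV-A fold increase with n = 226. These reproduce as t(0.975, 225) × SD × √2 / √226 = 0.0556 and 0.0742. At SD 0.4 this gives (7.59, 10.68) for 9-fold and (10.12, 14.23) for 12-fold, against the stated (7.6, 10.7) and (10.1, 14.2). The figure is maternal; no precision is stated for any infant endpoint.

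**2. Effect of pairing on a mean.** Take m mothers, a share t of whom contribute two infants, and within-pair correlation ρ. The number of infants is m(1 + t).

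- Variance assumed by the plan: σ² / [m(1 + t)]
- Actual variance: σ² [m(1 − t) + 2mt(1 + ρ)] / [m(1 + t)]²
- Ratio of actual to assumed: DE = 1 + 2tρ / (1 + t)

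The correct interval is √DE times the planned width, and the true coverage of the nominal 95% interval is about 2Φ(1.96/√DE) − 1. Neither t nor ρ is in the documents, so both are assumed. The ratio does not depend on how many mothers were enrolled.

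| t | ρ | DE | √DE | planned / correct width | coverage |
|---|---|---|---|---|---|
| 5% | 0.5 | 1.048 | 1.024 | 0.977 | 94.4% |
| 5% | 0.9 | 1.086 | 1.042 | 0.960 | 94.0% |
| 10% | 0.5 | 1.091 | 1.044 | 0.957 | 93.9% |
| 10% | 0.9 | 1.164 | 1.079 | 0.927 | 93.1% |
| 20% | 0.5 | 1.167 | 1.080 | 0.926 | 93.0% |
| 20% | 0.9 | 1.300 | 1.140 | 0.877 | 91.4% |

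The planned intervals are thus 2-4% too narrow at 5% twins, 4-7% at 10% and 7-12% at 20%.

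**3. On the log10 scale.** Take 226 mothers, SD 0.4 (borrowed from the maternal RSV-A assumption), t = 10% and ρ = 0.8. There are 226 × 1.1 ≈ 249 infants. The planned half-width is 0.0500; with clustering it is 0.0535.

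**4. Infant ANCOVA.** This was simulated with 226 and 113 mothers (252 and 126 less 10%) and a residual correlation of 0.8 after baseline and treatment, 3,000 runs per row. Simulation error on a coverage of 95% is √(0.95 × 0.05 / 3000) ≈ 0.4 percentage points.

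| t | coverage, ordinary SE | coverage, mother-clustered SE | SE ratio, clustered / ordinary |
|---|---|---|---|
| 5% | 94.3% | 94.9% | 1.03 |
| 10% | 93.1% | 94.8% | 1.06 |
| 20% | 92.1% | 95.2% | 1.12 |
| 30% | 91.0% | 95.2% | 1.16 |

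**5. Exact interval for ratio ≥ 1.** With 226 mothers, an assumed true proportion of 0.70, a latent correlation of 0.8 and 4,000 runs, coverage was 95.0% with no twins, 94.6% at 10% and 92.9% at 30%. At 10% the loss is within simulation error.

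**6. Later visits.** Protocol Amendment 1 stopped infant sampling at Days 43, 121 and 181. Samples already taken are paired only if both twins fell in the same sub-cohort. Protocol 1.2 describes allocation through the mother, while SAP 4.3.2.1 describes assignment of each infant, so the documents leave this open.

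**The case against.** The strongest objection is that the documents read as one infant per mother. The sub-cohorts in Protocol Table 5 sum to 3 × 84 + 3 × 42 = 378, the number of mothers. Table 14 gives 378 for the delivery read-out including cord blood, and Protocol 6.3.1 speaks of a single infant. If only one cord sample per delivery were analysed, the birth intervals would be unaffected. This stands as a condition on the finding but does not remove it: the numbers are approximate, the set definitions admit every infant with data, and nothing says which twin would be used.

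Second, everything is descriptive (SAP 2), there is no infant precision target and enrolment has stopped. That limits the consequence, and it stands. Third, SAP 4.3.3 calls its modelling exploratory and the code adjustable. The flexibility described concerns covariates, and it does not reach the intervals in 4.1.1 or the primary ANCOVA in 4.2.2.1.

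A reader might also infer three stronger claims that the documents do not support:

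- **Every infant antibody interval is affected.** Step 6 shows this is not established for the later visits.
- **The ANCOVA counts the mother's baseline twice.** A covariate shared within a pair is ordinary; a mixed model would use it in the same way.
- **Giving a twin pregnancy two votes is an error.** The endpoint is a percentage of infants, so equal weight per infant matches it.

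**Conclusion.** The point holds in conditional form. The plan admits twins, keeps all infants with data and has no method for pairs. Where both twins supply a birth sample, the intervals for birth GMT/GMC, the geometric mean transfer ratio, the percentage with ratio ≥ 1 and the infant ANCOVA are too narrow. The direction follows from positive within-pair correlation; the size rests on assumed twin shares and correlations. At 5-10% twins it is a few percent of interval width, with no material coverage loss shown for the exact interval at 10%. Nothing in the documents supports a particular twin share, so the 20% row shows sensitivity and is not an expectation. The ANCOVA figures depend on the residual correlation, which may be lower than the raw one. No test, sample size or stated decision rule changes.

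**What to change.** In SAP 4.1.1, 4.2.2.1 and 4.3.3:

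1. State that all sampled infants are analysed with equal weight per infant, and report how many mothers contribute two.
2. Take the intervals for infant GMT/GMC, the transfer ratio and the ANCOVA from a model with standard errors clustered on the mother. This leaves the point estimates as planned. A random mother effect is an alternative if there are enough pairs, though it gives each twin somewhat less weight than a singleton.
3. Use a cluster-adjusted interval for the percentage with ratio ≥ 1, for example Clopper-Pearson at the effective sample size.
4. Apply the same rule to Day 43/121/181 samples already collected if twins share a sub-cohort.
5. Keep averaging of twins to one value per mother as a sensitivity analysis only, since it changes the target from infants to mothers.

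The cost is a few lines of SAP text and code; maternal and infant identifiers are already linked (Protocol 6.3.1). The intervals become slightly wider, and with few pairs a random-effect variance may be poorly estimated, which favours the clustered standard errors.

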4.4. Tertiary Endpoint(s) Analyses

CCI
[Redacted text block]

4.5. Other Safety Analyses

Other safety analyses will be based on the Exposed Set, unless otherwise specified.

4.5.1. COVID-19 Assessment and COVID-19 AEs

A participant is defined as having a suspected, probable or confirmed COVID-19 infection during the study if the answer is “Confirmed”, “Probable” or “Suspected” to the case diagnosis question from the COVID-19 coronavirus infection assessment electronic Case Report Form (eCRF).

Numbers and percentage of participants with a suspected, probable or confirmed COVID-19 infection will be summarized by group based on Exposed Set.

Number and percentage of participants who had a COVID-19 test performed and number and percentage of participants with positive, negative and indeterminate results will be summarized by group on Exposed Set.

4.5.2. Additional Safety Assessments (if applicable)

Vital signs will be summarized by group using descriptive statistics at all timepoint(s). The information is collected on Exposed Set and Per-protocol Set. The parameters include but may not be limited to systolic blood pressure (SBP), diastolic blood pressure

(DBP), temperature, heart rate, respiratory rate, height, weight and body mass index (BMI).

4.5.3. Combined solicited and unsolicited events

The combined analysis of solicited and unsolicited events will be performed on Exposed Set. A summary of participants with all combined solicited and unsolicited adverse events will be provided.

Solicited adverse events will be coded by MedDRA as per the following codes

Solicited symptom	Lower level term code	Corresponding Lower level term decode
Pain	Injection site pain	10022086
Redness	Redness at injection site	10022098
Swelling	Swelling at injection site	10053425
Fatigue	Fatigue	10016256
Fever	Fever	10016558
Nausea	Nausea	10028813
Vomiting	Vomiting	10047700
Diarrhea	Diarrhea	10012727
Abdominal pain	Abdominal pain	10000081
Headache	Headache	10019211

Please note – to check for AE term in CDISC during dry run

For clintrial.gov and EudraCT posting purposes, a summary of combined solicited and unsolicited adverse events will be produced by System Organ Class and preferred terms and according to occurrence of each event.

4.6. Other Analyses

4.6.1. Other analyses for adolescent maternal participants

Sub-analyses to evaluate objectives and endpoints will be performed on the 15-17 Years of Age (YOA) sub-group.

4.6.1.1. Safety

Due to small number of adolescent maternal participants in this trial, a Bayesian approach will be applied to predict the probability of AEs in this population. It is assumed a specific AE in an adolescent maternal participant receiving the RSV-MAT vaccine is a binary outcome (yes/no) with p as a probability that the outcome is “yes”; it is further assumed that p is a random variable having beta distribution as a prior, which will be estimated from other data sources. The prior beta distribution will be developed based on data collected in RSV-MAT vaccine recipients above 17 YOA in this trial. With the data observed in RSV-MAT vaccine recipients 15-17 YOA, a Bayesian approach will be applied to estimate the posterior distribution of p . Similar procedures will be used for estimating the posterior distribution of p_0 (the probability of having this AE for an adolescent maternal participant in placebo group). However, the prior distribution for p_0 will be assumed as a mixture of beta distributions based on both the data collected in participants above 17 YOA in the placebo group in this trial and the adolescents younger

than 17 YOA in EPI-RSV-015 study [EPI-RSV-015, 2020]. Lastly, the predictive probability of the occurrence of this AE in an adolescent maternal participant 15-17 YOA will be calculated separately in the RSV-MAT vaccine group and the placebo group. A predictive probability in an adolescent maternal participant in RSV-MAT vaccine group no worse than that in placebo group will provide reassurance that vaccination does not result in higher risk of AE.

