**** Due to the recent safety signal, the study was fully unblinded to ensure the safety monitoring of the participants.***

Maternal participants 15 to 49 years of age (YOA) (inclusive, at the time of the study intervention administration) will be enrolled to receive either RSV maternal (RSV MAT) vaccine (120 µg of RSVPreF3) or the placebo control, between the 24^{0/7} to 36^{0/7} weeks of gestation (inclusive).

Approximately 378 eligible maternal participants will be enrolled* and randomized (2:1) to receive either RSV MAT vaccine or the placebo control. At least eighteen (5%) of the enrolled and randomized maternal participants will be between 15 and 17 YOA, inclusive. At the same time, infant participants (as yet unborn) will be further randomized (1:1:1) into sub-cohorts for blood sample collection for the assessment of immunogenicity at one of 3 timepoints (Day 43, Day 121 or Day 181 post-birth).

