9.4.6.2.1. Safety

Due to small number of adolescent maternal participants in this trial, a Bayesian approach will be applied to predict the probability of AEs in this population. It is assumed a specific AE in an adolescent maternal participant receiving the RSV-MAT vaccine is a binary outcome (yes/no) with p as a probability that the outcome is “yes”; it is further assumed that p is a random variable having beta distribution as a prior, which will be estimated from other data sources. The prior beta distribution will be developed based on data collected in RSV-MAT vaccine recipients above 17 YOA in this trial. With the data observed in RSV-MAT vaccine recipients 15-17 YOA, a Bayesian approach will be applied to estimate the posterior distribution of p . Similar procedures will be used for estimating the posterior distribution of p_0 (the probability of having this AE for an adolescent maternal participant in placebo group). However, the prior distribution for p_0 will be assumed as a mixture of beta distributions based on both the data collected in participants above 17 YOA in the placebo group in this trial and the adolescents younger than 17 YOA in EPI-RSV-015 study [EPI-RSV-015, 2020]. Lastly, the predictive probability of the occurrence of this AE in an adolescent maternal participant 15-17 YOA will be calculated separately in the RSV-MAT vaccine group and the placebo group. A predictive probability in an adolescent maternal participant in RSV-MAT vaccine group

no worse than that in placebo group will provide reassurance that vaccination does not result in higher risk of AE. The detailed analysis plan will be described in the protocol and SAP.

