5. SAMPLE SIZE DETERMINATION

Approximately 378 maternal participants* will be randomized in a 2:1 ratio to achieve at least 340 evaluable maternal participants (including at least 16 evaluable adolescents from 15 to less than 18 YOA).

Participants who withdraw from the study will not be replaced.

**** Due to the recent safety signal in RSV-MAT-009, there will be no further enrollment and vaccination of maternal participants.***

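### The adolescent Bayesian safety analysis adds external adolescents to the placebo prior only, so its reassurance verdict can be driven by that prior, in either direction

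*SAP*

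**What the plan says.** SAP 4.6.1.1 repeats Protocol 9.4.6.2.1 almost word for word. For the vaccine arm: "The prior beta distribution will be developed based on data collected in RSV-MAT vaccine recipients above 17 YOA in this trial". For placebo, the prior "will be assumed as a mixture of beta distributions based on both the data collected in participants above 17 YOA in the placebo group", to which the plan adds a second source, in the Protocol's wording "and the adolescents younger than 17 YOA in EPI-RSV-015 study". Each prior is updated with that arm's 15–17-year-olds, and one predictive probability per arm is calculated. The conclusion attached is: "A predictive probability in an adolescent maternal participant in RSV-MAT vaccine group no worse than that in placebo group will provide reassurance". The stated reassurance is about the vaccine adding no adverse event (AE) risk.

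Neither document gives the mixture weight, the effective sample size of any component, the external event rate, the AEs covered, a margin, a probability threshold, or a sensitivity analysis with matched priors. The Protocol defers the detail to the protocol and SAP, and the SAP adds none.

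The group is small. Protocol 1.2 plans: "At least eighteen (5%) of the enrolled and randomized maternal participants will be between 15 and 17 YOA, inclusive". SAP 5 expects the evaluable total to be reached "including at least 16 evaluable adolescents from 15 to less than 18 YOA". Enrolment has since stopped, and the number of adolescents actually enrolled is not stated.

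**The concern.** Let p be the adolescent AE probability under vaccine and p0 the same under placebo. If the external adolescents have a different AE rate from the trial adults, p0 moves towards that rate and p does not. The two predictive probabilities then differ with no vaccine effect at all.

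A difference is plausible. Under Protocol 5.1.1 the trial adults must have HIV and/or an obstetric complication, while the adolescents must be healthy. The external source is a retrospective database cohort, whereas trial events come from eDiaries and questioning at visits, so ascertainment may differ too.

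At stake is a pre-specified reassurance statement about pregnant minors, in a programme whose vaccination was stopped for a safety signal.

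A smaller mismatch adds to this. The adult sources are above 17 and the external source is below 17, so 17-year-olds inform neither prior. No lower age limit is given for the external group, although the target is 15–17.

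**Working it through.** **The plan's own figure.** The only safety sample-size figure is in SAP 5.1, the chance of at least one AE among 252: 1 − (1 − r)^252 gives 71.7%, 92.1% and 97.8% at r = 0.5%, 1% and 1.5%. This matches the stated 72%, 92% and 98%. No operating figure is given for the adolescent rule.

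**Inputs from the documents.** 378 at 2:1 is 252 vaccine and 126 placebo. Eighteen adolescents at 2:1 is 12 and 6, leaving 240 and 120 adults.

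**Assumptions.** Adult data enter at full weight. Event rates, external rate, external size and mixture weight are all assumed, because the documents give none of them.

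**Formulas.** For a prior Beta(a, b) and y events in n adolescents, the predictive probability is (a + y)/(a + b + n). For the placebo mixture it is the average of the two component values, with weights updated by each component's marginal likelihood. The rule is met if the vaccine value is at or below the placebo value.

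**One dataset, three priors.** Assume adults 30/240 vaccine and 12/120 placebo, adolescents 2/12 and 1/6.

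- Vaccine: (30 + 2)/(240 + 12) = 32/252 = 12.7%.
- Placebo, adults only: (12 + 1)/(120 + 6) = 13/126 = 10.3%. Rule not met.
- Placebo, external component at 20%, size 200, weight 0.5: the external part is (40 + 1)/(200 + 6) = 19.9%, the updated weights are 0.469 and 0.531, and 0.469 × 10.3% + 0.531 × 19.9% = 15.4%. Rule met.
- Placebo, external component at 5%: 8.3%. Rule not met.

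Only the external component changed. At external rate 20% and weight 0.2 the placebo value is 12.4% and the rule is not met, so the unstated weight also decides the verdict.

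**Simulation, no true difference** (40,000 replicates, Beta(0.5, 0.5) starting prior; all trial rates 10%, external size 200, weight 0.5):

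| External rate | SAP priors: rule met | Adult-only in both arms |
|---|---|---|
| 5% | 18% | about 52% |
| 10% | 53% | about 52% |
| 15% | 83% | about 52% |
| 20% | 91% | about 52% |

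At weight 0.2 the effect is milder: 64–73% at external rates of 15–20%.

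**Simulation, harm in adolescents only** (adults 10% in both arms, placebo adolescents 20%, external size 1000 at 20%, weight 0.5):

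| Vaccine adolescent risk | SAP priors | Adult-only in both arms | Same mixture in both arms |
|---|---|---|---|
| 40% (doubled) | 91% | 40% | 11% |
| 60% (tripled) | 86% | 30% | 1% |

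For doubled risk, the SAP figure is 71% at external weight 0.2 and 99% at 0.8. External size 200 at weight 0.5 still gives 91%.

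**What asymmetry does not explain.** Adults make up 240/252 = 95% of the vaccine posterior. With 24/240 adult events, even 12/12 adolescent events gives only (24 + 12)/252 = 14.3%. This is why adult-only priors still reassure 40% of the time when adolescent risk doubles.

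**The case against.** Five points can fairly be made on the other side.

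1. **Direction.** A reader might infer that the plan is tilted towards declaring the vaccine safe. The documents do not support that, because no external rate is given. If adolescents and the external cohort run at 5% and adults at 10%, with no vaccine effect, the SAP rule reassures 13% of the time against 52% with adult-only priors. There the asymmetry works against the vaccine. This stands.

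2. **Size.** A reader might take 91% reassurance under doubled risk as the cost of the asymmetry. It is not: adult-only priors in both arms already give 40%. The scenario also assumes harm confined to adolescents. If adult risk doubles as well (20% v 10%), the SAP rule reassures only 5.5% of the time at weight 0.5. This stands.

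3. **Availability.** The documents describe no external vaccinated adolescents, so some asymmetry of data is unavoidable. This stands only in part: a shared background component with a treatment effect needs no such source.

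4. **Scope.** The title of the external study describes pregnancy outcomes and events of interest. Solicited reactions may have no external component, and the asymmetry then does not arise for them. This stands.

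5. **Weight.** SAP 2 makes every analysis descriptive, this one sits under other analyses, and SAP 4.2.1.1 and 4.6.2 provide observed summaries for those under 18 by study group. This stands, and limits the seriousness.

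**Conclusion.** The unequal prior sources are explicit in both documents, and no matched-prior analysis offsets them. As written, the rule can give opposite verdicts on identical adolescent and adult data, so a reassurance statement resting on it is not supported.

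With no true difference, the chance of reassurance runs from 18% to 91% across external rates of 5% to 20%, against about 52% with adult-only priors in both arms. With adolescent risk doubled and adults unaffected, it is 91%, against 40% with adult-only priors and 11% with the same mixture in both arms. These figures depend on assumed rates, weights, external size, full-weight adult data and the planned 12/6 split. They show what can happen, not what will.

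The point concerns AEs that the external cohort records. It touches no primary result or formal test. It should be corrected before analysis, but it does not undermine the trial's main safety summaries.

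**What to change.** - Use the same prior sources in both arms. The preferred form applies one external adolescent component to the background risk of both arms, with a separate treatment effect.
- Report the arm-specific adult-only result beside it as a sensitivity analysis. It should not be the sole replacement, since adult data then dominate both arms.
- Pre-specify the mixture weight and the effective sample size of each component.
- List the AEs for which the external cohort supplies data.
- Match the external age band to 15–17.
- Replace the point comparison, which is met about half the time under no difference even with adult-only priors in both arms, with the posterior of p − p0, including P(p > p0).

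The cost is SAP wording and code for one descriptive analysis, with no new trial data. The downside is a little more analysis work and a reassurance statement that is harder to make.
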